## 9. SAFETY MEASUREMENTS

### 9.1. Definitions

All unanticipated problems will be reported in this study. The Committee For the Protection of Human Subjects (CPHS) considers unanticipated problems to be any incident, experience, or outcome that meets all of the following criteria:

- unexpected in terms of nature, severity, or frequency given a) the research procedures that are described in the IRB-approved research protocol and informed consent, and b) the characteristics of the subject population being studied;
- related or possibly related to participation in the research (possibly related means there is a reasonable possibility that the incident, experience, or outcome may have been caused by the procedures involved in the research); and
- places subjects or others at a greater risk for physical, psychological, economic, or social harm than was previously known or recognized.

An incident, experience, or outcome that meets the 3 criteria above will generally warrant consideration of substantive changes in order to protect the safety, welfare, or rights of subjects or others. Examples of corrective actions or substantive changes that might need to be considered in response to an unanticipated problem include the following:

- changes to the research protocol initiated by the investigator prior to obtaining IRB approval to eliminate apparent immediate hazards to subjects
- modification of inclusion or exclusion criteria to mitigate newly identified risks
- implementation of additional procedures for monitoring subjects
- suspension of enrollment of new subjects
- suspension of research procedures in currently enrolled subjects

For this study, an severe adverse event (SAE) is defined as an unanticipated problem occurring during the study that fulfills 1 or more of the following criteria:

1. Results in death
2. Is immediately life-threatening†
3. Requires inpatient hospitalization or prolongation of existing hospitalization
4. Results in persistent or significant disability or incapacity
5. Is a congenital abnormality or birth defect
6. Is an important medical event that may jeopardize the subject or may require medical intervention to prevent one of the outcomes listed above

Hospitalization for elective procedures or surgeries will not be considered SAEs, nor will inpatient hospitalizations for convenience.

Pregnancy in women with childbearing potential should not be reported as an SAE, but if pregnancy occurs, it must be reported in accordance with the procedures described in Section 6.2. Pregnancy will not be regarded as an SAE unless there is suspicion that a study intervention may have interfered with the effectiveness of a contraceptive medication and the event meets the criteria for an unanticipated problem. If the pregnancy results in an outcome other than a normal birth or elective abortion of a healthy fetus, it will be reported as an SAE.

### 9.2. Collecting, Recording and Reporting of Adverse Events

Examination and close follow-up of parameters capturing subjects' oral health will be collected on case report forms (CRFs). These will be completed at every study visit, and data will be compiled into a pre-specified format and reviewed monthly by

the PI for safety oversight.

Serious adverse events (as defined in Section 9.1) will be collected from the time of enrollment until the last clinic visit and will be recorded in the electronic health records (EHR) system. At each study visit, the study staff will inquire about the occurrence of SAEs since the last assessment. The investigator will review all source documentation related to study procedures for evidence of SAEs. Events will be followed for outcome information until they return to baseline or stabilize, or until 30 days after study completion or subject discontinuation. Subjects who have an SAE that is ongoing 30 days after study completion or discontinuation will be referred to an appropriate practitioner for continued care.

Upon learning that a subject has experienced an SAE, the investigator must report the event to CPHS within 24 hours after becoming aware of the event.

On a monthly basis, the following events will be reported to every PI:

█ number of subjects meeting criteria for implant failure and number of subjects enrolled.

█ duration of observation of subjects meeting implant failure criteria and duration of observation of subjects enrolled

█ for subjects having failed implants:

- Criteria for failure implants
- Baseline enrollment and interim visit information

█ any tooth loss, abscess, or other adverse oral health development requiring therapy or other intervention and the etiology (as captured in the dental history)  
Every PI will review the monthly reports for any safety signals.

### **9.3. Safety Monitoring Plan**

The purposes of the clinical monitoring activities are to ensure that the rights of human subjects are protected, the study is implemented in accordance with the protocol, and the integrity of study data is maintained.

All subjects will be monitored for postoperative healing and tissue response at a regular interval while the entire oral health will be maintained throughout the study period.

## **10. DATA ANALYSIS**

### **10.1. Data Quality Assurance**

Data and measurements will be checked by two separate sub-investigators ([name], [name]) as well as analyzed statistically to ensure that the data obtained is accurate, complete and reliable.

### **10.2. Data Entry and Storage**

Case report forms (CRFs) will be completed and stored in a locked file cabinet in the PI's office located at UTSD. Data will be entered electronically in excel spreadsheets, and images will be stored electronically; both will be stored on the PIs work computer in a locked office and password protected.

## 11. SAMPLE SIZE AND STATISTICAL METHODS

### 11.1. Determination of Sample Size

Hypothesis:

H1: Ridge dimensional reductions in the sites of immediate implant combined with autogenous tissue graft/acelluar dermal matrix are significantly less than the sites of immediate implant alone.

Null hypothesis:

H0: Ridge dimensional reductions in the sites of immediate implant combined with autogenous tissue graft/acelluar dermal matrix are not significantly less than the sites of immediate implant alone.

Significance Tests:

If significance tests generate 95% likelihood that the results do not fit the null hypothesis (H0), then it is rejected, in favour of the alternative (H1).

Otherwise, the null is accepted. These are the only correct assumptions, and it is incorrect to reject, or accept, H1.

Accepting the null hypothesis does not mean that it is true. It is still a hypothesis, and must conform to the principle of falsifiability, in the same way that rejecting the null does not prove the alternative.

Calculation of Sample Size:

Based on the data published in the articles and preliminary results, we have calculated that 11 subjects per group need to be recruited in order to have 80% power to detect a 1mm difference with 0.9 mm standard deviation in ridge dimensional change between the immediate implant alone group and the other two groups (Faul et al. 2009). We plan to enroll a total of 42 subjects (14 subjects in each group) to account for potential dropout.

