### **3. STUDY POPULATION**

#### **3.1. List the number of subjects to be enrolled.**

**The primary outcome is ridge dimensional alteration at six months after surgery while the secondary outcomes are changes of gingival level, gingival thickness, width of keratinized gingiva, alveolar bone level and bone dimension.** Based on the preliminary results, 11 subjects per group need to be recruited to have 80% power to detect a 1 mm difference with 0.85 mm standard deviation in ridge dimensional change between groups. We plan to enroll 14 subjects in each group to account for potential dropout. The subjects will be recruited from the patients enrolled in the clinics of University of Texas Health Science Center at Houston School of Dentistry (UTSD) and Periodontal and Implant Surgeons of Houston (PISH). There will be no restriction on gender or race.

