### **3.6. Subject Replacement**

Subjects who withdraw from the study can be replaced. However, to complete the study within the time allocated, centers will not enroll subjects after 24 months from enrollment initiation.

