## **5. STUDY DESIGN**

## 5.1. Summary of Study Design

We propose to conduct a randomized controlled trial with three treatment arms: immediate implant, immediate implant combined with SCTG, and immediate implant combined with ADM. Patients (age $\geq$ 18 year-old) need to have single maxillary unrestorable tooth which is planned to be replaced with an implant in the esthetic zone (maxillary premolar to premolar). The unrestorable tooth has adjacent teeth and acceptable periodontal condition (probing depth  $\leq$ 4mm, gingival recession $\leq$  1mm at six sites: mesial-buccal, mid-buccal, distal-buccal, distal-palatal, mid-palatal, distal-palatal). The patients have to be systemically healthy or have controlled common systemic conditions (controlled hypertension, controlled diabetes HbA1c up to 7 %). Smokers having cigarettes  $\leq$  10/per day are eligible but they are encouraged to stop smoking 1 week prior to and up to 2 months after implant placement (Bain, 1996). The primary outcome of the study is the ridge dimensional alterations at six months and 12 months after surgery while the secondary outcomes are the changes of gingival level, gingival thickness, width of keratinized gingiva, alveolar bone level, and bone dimension.

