- 8) Buccal-palatal dimension of the ridge at the site of implant placement: the dimension will be measured at different reference points (3 mm, 6 mm from the baseline gingival margin) on the study model. Impressions for study models will be taken at the first visit, at 3 months, 6 months and 12 months. The measurement will be done by the digital caliper and the computer assisted scanned images.
- 9) Buccal plate thickness: it will be measured on the images of dental cone beam computed tomography. The patients will have the images taken with a stent before the surgery and 6 months after the surgery. The stent will be made based on the patient's dental model. The midline of the implant site will be buccally and palatally marked with gutta percha.
- 10) Interproximal bone level: a film holder with silicon putty to aid in reproducibility of the radiograph position will be used. The mesial and distal crestal bone level will be measured using the MIPACS software. Implant platform will serve as the reference point. Vertical and horizontal changes (depth and width of the vertical defect on the mesial and/or distal aspect of the implant, if present) will also be measured from radiographs taken at the time of completion of surgery, at 6 and 12 months. Dose and frequency of x-rays in the study are standard of care for any implant patient in UTSD, PISH or in standard clinical practice, and are not altered for the purpose of the study. (Medical status is updated and recorded at each visit, including verification that female patients are not pregnant prior to x-ray taking; this is also standard of care).
- 11) The diameter of the apical radiolucency, when initially present, will be monitored radiographically. Any lesions present in the radiography will be assessed immediately after surgery and 6 months.
- 12) Blood flow of gingiva: The laser Doppler flowmeter is a noninvasive measure of capillary blood perfusion. The readings are obtained by placing the tip on the

surface of buccal gingival. It is measured before and after implant surgery at the first visit, 3 months, 6 months and 12 months.

*c. Final Study Visit:*

The 12-month follow-up will be the subject's last visit for this clinical trial. The patients will have clinical measurements (PD, BOP, PI), dental impressions taken, and periapical radiographic examination. All subjects will have periodontal maintenance in the periodontics clinic of UTSD or PISH in the future.

*d. Post Study Follow up and Procedures*

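### The 80% power stated for 11 per group is not the power of the planned one-way ANOVA (73–78%), and Sections 3.1 and 11.1 reach the same 11 from different standard deviations

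*Combined protocol and SAP*

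**What the plan says.** Section 11.1 (sample size) says that "11 subjects per group need to be recruited in order to have 80% power to detect a 1mm difference with 0.9 mm standard deviation", and describes the comparison as "in ridge dimensional change between the immediate implant alone group and the other two groups". It cites a power program but names no test and no sidedness. Its alternative hypothesis is directional: reductions with a graft "are significantly less than the sites of immediate implant alone".

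Section 3.1 repeats the calculation with another standard deviation: "11 subjects per group need to be recruited to have 80% power to detect a 1 mm difference with 0.85 mm standard deviation". Both sections enrol 14 per group to allow for dropout and give no dropout rate.

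Section 11.2.c names one between-group test, a one-way ANOVA across the three groups. It sets the level at 0.05 and adds Bonferroni corrections for multiple comparisons, without saying what is being corrected for. It also says that data from withdrawn patients will be analysed.

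The primary endpoint itself differs between sections. Section 3.1 says the "primary outcome is ridge dimensional alteration at six months after surgery". Section 5.1 says: "The primary outcome of the study is the ridge dimensional alterations at six months and 12 months after surgery". For the ridge measurement, Section 6.3.b (item 8) says "the dimension will be measured at different reference points (3 mm, 6 mm from the baseline gingival margin) on the study model" and does not say which point is primary.

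**The concern.** A stated power should belong to the test that will be run. Here the sizing test is unnamed, and the 80% does not match the only between-group test in the plan. Two sections also give different standard deviations for what is presented as one calculation, so at least one of them does not describe how 11 was obtained.

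What is at stake is how the result is read. A significant overall F shows that the three means are not all equal. It does not show that a given graft loses less ridge than implant alone, which is what the hypothesis asserts. That claim needs comparisons with control, and their sidedness and family are not given. After a non-significant result, the plan as written does not tell the reader how likely a true 1 mm effect was to be missed.

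**Working it through.** **Inputs.** Difference 1 mm (Sections 3.1 and 11.1); SD 0.85 mm (3.1) or 0.90 mm (11.1); n = 11 needed and 14 enrolled per group (both); level 0.05 (11.2.c). Group means are taken as (0, 1, 1): Section 11.1 sets implant alone against both other groups, and Section 2.1 expects the two grafts to be comparable. One time point and one reference point are assumed unless stated. All power figures are exact (noncentral t or F).

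**Step 1: reproduce the 11.**

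- One-sided two-sample t-test at 0.05: noncentrality δ = (1/SD)·√(n/2), df = 2n − 2. At SD 0.90 and n = 11, δ = 1.111 × 2.345 = 2.606, critical t = 1.725, power 80.8%. The minimum n for 80% is 11.
- Two-sided contrast of control (n) against both grafts together (2n) at 0.05: δ = (1/SD)·√(2n/3). At SD 0.90 and n = 11, δ = 1.111 × 2.708 = 3.009, power 83.0%. The minimum n is again 11.
- Two-sided two-sample t-test at 0.05: power 69.8% at 11 and minimum n = 14, so it does not reproduce 11.

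At SD 0.85 the two tests that give 11 have 84.6% and 87.0% at n = 11, and each needs only 10. The 11 is therefore tied to SD 0.90, not to the figure in Section 3.1.

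**Step 2: the planned ANOVA.** λ = n·Σ(μᵢ − μ̄)²/SD², df = 2 and 3(n − 1). For means (0, 1, 1), Σ(μᵢ − μ̄)² = (2/3)² + 2(1/3)² = 2/3. At n = 11 and SD 0.90, λ = 11 × 0.667/0.81 = 9.05, critical F(2, 30) = 3.316, power 72.8%. At SD 0.85, λ = 11 × 0.667/0.7225 = 10.15, power 77.9%.

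| Evaluable per group | ANOVA F, SD 0.85 | ANOVA F, SD 0.90 |
|---|---|---|
| 11 | 77.9% | 72.8% |
| 12 | 81.9% | 77.1% |
| 13 | 85.3% | 80.8% |
| 14 | 88.2% | 84.1% |

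The minimum n for 80% is 12 (SD 0.85) or 13 (SD 0.90). The difference detectable with 80% power is 1.03 / 1.09 mm at 11 and 0.90 / 0.95 mm at 14 (SD 0.85 / 0.90).

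The pattern (0, 1, 1) is not a harsh choice. With one graft midway, (0, 0.5, 1), ANOVA power at 11 is 64.7% / 59.5%.

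**Step 3: the claim for each graft.** This step is conditional on Bonferroni covering either the two graft-versus-control comparisons (0.05/2 = 0.025) or all three pairs (0.05/3 = 0.0167). Ranges run from the lowest power (three pairs, two-sample df 2n − 2) to the highest (two comparisons, pooled ANOVA error with df 3n − 3).

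| Power per graft | SD 0.85 | SD 0.90 |
|---|---|---|
| n = 11, two-sided | 57–66% | 51–60% |
| n = 11, one-sided | 68–76% | 63–71% |
| n = 14, two-sided | 71–78% | 65–73% |
| n = 14, one-sided | 80–86% | 75–82% |

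**Step 4: two primary time points.** If 6 and 12 months are both primary and 0.05 is split equally, ANOVA power per time point is 67.6% / 61.6% at 11 and 80.9% / 75.5% at 14 (SD 0.85 / 0.90).

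**The case against.** The strongest reply is that the 11 is a correct calculation under two natural readings of Section 11.1. The one-sided t-test fits the directional hypothesis, and the contrast of control against both grafts fits the phrase about the other two groups. The contrast can also be carried out within a one-way ANOVA. On this view the fault is incomplete specification, not wrong arithmetic. That is right as far as it goes, but Section 11.2.c mentions neither a contrast nor one-sided testing, so the plan does not secure the 80%.

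Second, enrolment of 14 covers the ANOVA. Section 3.6 adds that "Subjects who withdraw from the study can be replaced", and withdrawn patients' data are to be analysed. This stands for the overall F at one time point, provided at least 13 per group (SD 0.90) or 12 (SD 0.85) are evaluable. It fails if the full allowance of 3 in 14 (21%) is lost without replacement, and replacement stops with the 24-month enrolment limit.

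Third, the per-graft figures depend on a family the plan does not state, and power to show a benefit for at least one graft is higher: with two-sided tests and pooled error, about 69–80% at 11 and 82–90% at 14. This too is fair. The per-graft figures are conditional, and the low end should not be read as the trial's power. But the plan does not say whether one graft or each graft must succeed, and requiring both would give only 38–51% at 11.

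Fourth, the SD discrepancy does no harm by itself, because Section 11.1 uses the larger value. Agreed, but the two sections still need to agree.

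**Conclusion.** The concern holds. The 80% at 11 per group is not the power of the one-way ANOVA, which is 72.8% (SD 0.90) or 77.9% (SD 0.85). Sections 3.1 and 11.1 give different SDs for the same 11, and only 0.90 makes 11 the minimum under either test that reproduces it. These conclusions rest on a full 1 mm benefit of both grafts, equal group sizes and a single primary time point.

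For the overall F the practical loss is small: 84–88% with all 14 per group evaluable. For a claim about each graft the shortfall is larger, though conditional on sidedness and family. With two-sided corrected comparisons, power stays below 80% even at 14 per group, at either SD and for either family considered. This should be fixed, but it does not put the design in doubt.

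**What to change.** 1. Reconcile the primary time point between Sections 3.1 and 5.1, and state whether the 3 mm or the 6 mm reference point is tested.
2. Use one SD in Sections 3.1 and 11.1 and give its source.
3. In Sections 11.1 and 11.2.c, name the test that supports the primary claim, its sidedness, and what the Bonferroni family contains.
4. Restate power and detectable difference for that test at 11 and 14 evaluable per group, leaving enrolment as it is. At SD 0.90 and one time point:

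| Primary test | Power at 11 | Power at 14 | Detectable with 80% power, 11 / 14 |
|---|---|---|---|
| (a) One two-sided contrast, implant alone against both grafts | 83% | 91% | below 1 mm at both |
| (b) One-way ANOVA | 73% | 84% | about 1.09 / 0.95 mm |
| (c) Two two-sided graft-versus-control comparisons | 58–60% | 71–73% | about 1.25 / 1.09 mm |
| (d) Three two-sided pairs | 51–53% | 65–67% | about 1.32 / 1.15 mm |

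All are lower if the family also spans time points or reference points.

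The cost is wording in Sections 3.1, 5.1, 11.1 and 11.2.c, with no extra patients and no change in conduct. Under (b), (c) or (d) the stated power at 11 becomes less favourable. Option (a) keeps 11 as it stands but gives up a primary claim for either graft alone.

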### 11.2. Statistical and Analytical Plans

#### a. General Considerations

We will present means and standard deviations for completeness of the report. The statistical significance level to test the primary endpoint was set at  $p<0.05$ , a priori.

## **12. ETHICAL CONSIDERATIONS**

### **12.1. Informed Consent**

Informed consent is a process that is initiated prior to the individual's agreeing to participate in the study and continues throughout the individual's study participation. Extensive discussion of risks and possible benefits of study participation will be provided to the subjects and their families. A consent form describing in detail the study interventions, procedures, and risks will be given to the subject. Consent forms will be IRB-approved, and the subject will be asked to read and review the document. The investigator or designee will explain the research study to the subject and answer any questions that may arise. The subject will sign the informed consent document prior to any study-related assessments or procedures. Subjects will be given the opportunity to discuss the study with their surrogates or think about it prior to agreeing to participate. They may withdraw consent at any time throughout the course of the trial. A copy of the signed informed consent document will be given to subjects for their records. The rights and welfare of the subjects will be protected by emphasizing to them that the quality of their clinical care will not be adversely affected if they decline to participate in this study.

The consent process will be documented in the clinical or research record. This documentation will include the following:

- notation of the date that the consent was obtained
- statement that the consent was obtained prior to the initiation of study procedures
- statement that the subject had adequate time to review the consent and that all questions were answered prior to initiation of study procedures
- notation confirming that a copy of the signed consent was given to the subject

## **12.2. IRB review**

The protocol, informed consent form(s), and all advertising and subject materials will be submitted to the IRB for review and approval. Approval of both the protocol and informed consent form must be obtained before the enrollment of any subject. Any amendment to the protocol will require review and approval by the IRB before the changes are implemented in the clinic.

## **12.3. Confidentiality of Data and Patient Records**

The subject's name will appear only on the consent form and clinical record, both of which will be kept separate from collected study data. All subject files will be kept confidential and placed in a double-locked office. A unique coded study number will be assigned to each subject for data collection. The number will not contain any personal information (e.g., dates, age) to further ensure protection.

The study protocol, documentation, data, and all other information generated will be held in strict confidence. No information concerning the study or the data will be released to any unauthorized third party without prior written approval of the PI. No subject names will be used in publications or presentations.

